9.5 SAFETY ANALYSES

The FAS will be the primary analysis set for safety evaluation. Safety will be assessed by AEs, ECG and laboratory test measurements.

AEs will be coded using the Medical Dictionary for Regulatory Activities (MedDRA) version 16.1 or higher and graded according to NCI-CTCAE Version 4.03. If the AE is not included in the NCI-CTCAE Version 4.03, the Investigator will assign a grade according to [Section 8.2.1](#).

The focus of AE summaries will be on TEAEs. A TEAE is defined as any AE that emerges or worsens in the period from the first dose of study treatment to 30 days after the last dose of study treatment. AEs will be summarized by the frequency of subjects experiencing TEAEs by MedDRA system organ classes (SOC) and preferred terms (PT). Separate tabulations will also be

produced for drug-related AEs, SAEs, AEs that led to treatment discontinuation, and AEs of at least Grade 3 severity.

ECG measurements will be tabulated for changes over time on study.

Laboratory parameters will be summarized for changes over time by descriptive statistics, and laboratory values that are of Grade 3 severity or greater will be tabulated and listed on an individual subject basis.

9.6 PHARMACOKINETIC ANALYSES

Plasma samples will be analyzed for IPI-145 and potential metabolite concentrations using a validated high performance liquid chromatography-tandem mass spectrometry (LC/MS/MS) method.

The PK data collected will be analyzed by standard population PK methods, using appropriate software. The intent of this analysis is to obtain exposure data in subjects with indolent lymphoma, to characterize the parameters of PK disposition, and to identify relevant covariates affecting drug exposure. If there is only a limited amount of plasma concentration data from this study, the data may be pooled with the results of other studies to perform the population PK analysis.

Additional details on the pharmacokinetic methods and analysis will be provided in the SAP.

9.7 ANALYSIS OF OTHER ENDPOINTS

9.7.1 Biomarker Analyses

All biomarker analyses will be descriptive in nature. Summary tabulations may be produced if data from a sufficient number of subjects are collected. Additional details on the biomarker analysis methods will be provided in the SAP

9.7.2 Analyses of Health-Related QoL

Details on the analysis methods of health-related QoL endpoints will be provided in the SAP.

9.8 INTERIM AND FINAL ANALYSES

9.8.1 Interim Analysis

An interim futility analysis will be performed approximately 4 months after at least 30 subjects (25% of total) have initiated treatment with IPI-145. The futility boundary is non-binding, meaning that the Type I error will be properly controlled if the study continues after the futility boundary is crossed at the interim analysis. If the interim analysis occurs 4 months after exactly 30 subjects have initiated treatment, the one-sided p-value for futility is 0.6552. This is equivalent to a response rate of 26.4% or 7 responders or less out of the 30 subjects. Actual p-value boundary for futility will be calculated based on the number of subjects at the interim analysis by linear interpolation.

ORR based on the Investigator's assessment will be used for the interim analysis.

If the required total number of subjects are accrued for the interim analysis but follow-up is not sufficiently mature to reasonably assess the ORR, accrual may proceed while the data on interim analysis subjects are being collated.

An Independent Data Monitoring Committee (IDMC) will review ORR and other efficacy data at the planned interim analysis. Safety analyses will also be performed at this interim analysis. Further details will be contained in the IDMC charter.

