4 STUDY DESIGN

This is an open-label, single arm efficacy and safety study of IPI-145 administered orally to subjects who have been diagnosed with iNHL (FL, MZL, or SLL) whose disease is refractory to rituximab and to either chemotherapy or RIT. Approximately 120 subjects will be enrolled. Enrollment is anticipated at approximately 100 sites with approximately 40 sites in the US and the remainder of sites outside of the US. It is anticipated that the entire study will accrue subjects over approximately 30 months.

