9.1 SAMPLE SIZE DETERMINATION

This study will test the null hypothesis that the ORR is $\leq 30\%$ against the alternative that ORR is $\geq 45\%$. Using a group sequential design with 1 interim analysis, 120 subjects will provide $>90\%$ power to achieve a one-sided overall significance level of 0.025. The interim analysis will occur approximately 4 months after at least 30 subjects (25% of the total) have initiated treatment with IPI-145. The cumulative Type II error to be spent at the interim and final analyses are 0.02 and 0.1, respectively. The interim analysis is intended for futility only and hence no Type I error will be spent.

Among the 120 subjects to be enrolled, approximately 80 will be diagnosed with FL.

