9.4 EFFICACY ANALYSES

Assessment of response and progression status will be evaluated locally (i.e. Investigator's assessment) and by an independent, third party panel of radiologists and oncologists according to the revised IWG Response Criteria for Malignant Lymphoma¹. The independent response assessment will be used for the primary analyses of response and progression-based efficacy endpoints (i.e. ORR, PFS, TTR and DOR). Data based on local assessment will also be presented for these endpoints.

The FAS will be the primary analysis set for all efficacy analyses. The evaluable analysis set will also be used for some efficacy analyses, with details specified in the SAP.

Analyses for primary and secondary efficacy endpoints will be performed for the overall study population (iNHL), the follicular lymphoma population and subsets defined by other disease subtypes.

Analyses of the exploratory efficacy endpoint will be specified in the SAP.

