9.4.1 Analysis of Primary Endpoint

ORR will be tested against the null ($\leq 30\%$) by 1-sided exact binomial test at 0.025 level. The estimated ORR along with the 2-sided 95% exact confidence interval will be provided. Missing data will be imputed by assuming that any subjects not exhibiting a response (CR or PR) are non-responders.

ORR will also be presented for the follicular lymphoma population, as well as the other disease subtypes, with 2-sided 95% exact confidence intervals.

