3.4 INTERIM ANALYSIS

An interim futility analysis will be performed approximately 4 months after at least 30 subjects (25% of total) have initiated treatment with IPI-145. The futility boundary is

non-binding, meaning that the Type I error will be properly controlled if the study continues after the futility boundary is crossed at the interim analysis. If the interim analysis occurs 4 months after exactly 30 subjects have initiated treatment, the one-sided p-value for futility is 0.6552. This is equivalent to a response rate of 26.4% or 7 responders or less out of the 30 subjects. Actual p-value boundary for futility will be calculated based on the number of subjects at the interim analysis by linear interpolation.

ORR based on the Investigator's assessment will be used for the interim analysis.

If the required total number of subjects are accrued for the interim analysis but follow-up is not sufficiently mature to reasonably assess the ORR, accrual may proceed while the data on interim analysis subjects are being collated.

The following data will be reviewed by an external Independent Data Monitoring Committee (IDMC) at the interim analysis: ORR, time to response (TTR), disposition, demographics and baseline characteristics, prior anticancer therapy, medical history, concomitant medications, exposure, dose modifications, treatment-emergent adverse events (TEAEs), serious adverse events (SAEs), deaths, laboratory parameters, and additional data requested by the IDMC. Further details will be provided in the IDMC charter.

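### Does the futility rule need a stated stopping count for every interim sample size above 30?

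*Protocol*

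**What the plan says.** Protocol 9.1 and SAP 3.2 test an ORR of 30% or less against 45% or more, with 120 subjects, one-sided 0.025 and power above 90%. On the Type II error, protocol 9.1 says: "The cumulative Type II error to be spent at the interim and final analyses are 0.02 and 0.1, respectively".

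Protocol 9.8.1 times the look as follows: "An interim futility analysis will be performed approximately 4 months after at least 30 subjects (25% of total) have initiated treatment with IPI-145". For exactly 30 subjects it gives a one-sided futility p-value of 0.6552 and adds: "This is equivalent to a response rate of 26.4% or 7 responders or less out of the 30 subjects". For any other number it says: "Actual p-value boundary for futility will be calculated based on the number of subjects at the interim analysis by linear interpolation". SAP 3.4 repeats these statements.

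The interim and final analyses use different readers of response. For the interim, SAP 3.4 says: "ORR based on the Investigator's assessment will be used for the interim analysis". For the final analysis, protocol 9.4 says: "The independent response assessment will be used for the primary analyses of response and progression-based efficacy endpoints". The only ORR test named is the one for the primary endpoint in protocol 9.4.1, "by 1-sided exact binomial test at 0.025 level".

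The boundary is described as non-binding, and both documents leave further detail on the interim to the IDMC charter. Under protocol 10.7 the IDMC makes a recommendation on futility and the sponsor decides.

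**The concern.** The trigger is a minimum of 30 subjects, so a larger interim sample is foreseen. Linear interpolation needs two points, and the text gives one. It names no interim test, no variance and no count for n above 30. The obvious test to borrow, the exact binomial, does not fit the plan's own line: at 8 of 30 the exact p-value is 0.7186, above 0.6552, so it would stop at 8, whereas the plan stops at 7.

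Two analysts could therefore arrive at different stopping counts for the trial's only formal interim decision. The trial is open-label with investigator-assessed interim response, so one would want that count settled before the data are seen. At stake are the chance of wrongly stopping an active drug and the claim of power above 90%.

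**Working it through.** **Inputs.** From protocol 9.1: p0 = 0.30, p1 = 0.45, N = 120, one-sided alpha 0.025, cumulative Type II error 0.02 at the interim and 0.10 at the end. From protocol 9.8.1: p = 0.6552, 26.4% and 7 or fewer, all at n = 30.

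**Step 1. Reproduce the n = 30 boundary.** Take a two-look normal design with information fraction 30/120 = 0.25, non-binding futility and the stated Type II spend. It solves to a drift of 3.3085.

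- Interim z = z(0.02) + 3.3085 × √0.25 = −2.0537 + 1.6543 = −0.3995, so p = 0.6552, as printed.
- Required N = (3.3085/0.15)² × 0.45 × 0.55 = 120.4. With the null variance it would be 102.2.
- Boundary rate with the SE at 45%: 0.30 − 0.3994 × √(0.2475/30) = 0.2637, which is 26.4%. Since 30 × 0.2637 = 7.91, the count is 7 or fewer.
- With the null SE: 0.30 − 0.3994 × √(0.21/30) = 0.2666, which is 26.7%. With the observed variance the rate is 26.8%.

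Only the SE at 45% gives the printed rate, and it also gives the planned 120. The scale is unstated but recoverable.

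**Step 2. Counts above 30 on that scale.** The stopping count is the largest r for which the one-sided p-value of (r/n − 0.30)/√(0.2475/n) is at or above the boundary. Three interpolations are tried, each an assumption:

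- A: p runs linearly from 0.6552 at n = 30 to 0.025 at n = 120.
- B: p stays at 0.6552.
- C: cumulative Type II error runs linearly from 0.02 at n = 30 to 0.10 at n = 120 and is then converted to p.

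The final rule is 47 or more of 120 (exact alpha 0.0200; power 91.6% with no interim). Power with the interim is the sum over x > r of P(X = x | n, 0.45) × P(at least 47 − x responders among the other 120 − n). This treats investigator and independent response as the same, and assumes that the boundary is obeyed.

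| n | Count A | Count B | Count C | Power A | Power B | Power C |
|---|---|---|---|---|---|---|
| 30 | 7 | 7 | 7 | 91.0% | 91.0% | 91.0% |
| 31 | 8 | 8 | 8 | 90.3% | 90.3% | 90.3% |
| 32 | 8 | 8 | 8 | 90.7% | 90.7% | 90.7% |
| 33 | 8 | 8 | 9 | 91.0% | 91.0% | 89.9% |
| 34 | 9 | 9 | 9 | 90.5% | 90.5% | 90.5% |
| 35 | 9 | 9 | 9 | 90.8% | 90.8% | 90.8% |
| 40 | 11 | 10 | 12 | 90.7% | 91.3% | 89.4% |
| 45 | 13 | 12 | 14 | 90.7% | 91.3% | 89.4% |
| 50 | 14 | 13 | 16 | 91.3% | 91.5% | 89.4% |

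Over n = 31 to 50, A never falls below 90.3% (n = 31) and C never falls below 89.4%. The chance of stopping at a true ORR of 45% is at most 2.3% under A (n = 31) and 4.3% under C (n = 50).

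**Step 3. How far above 30 could n be?** Protocol section 4 says: "It is anticipated that the entire study will accrue subjects over approximately 30 months". If accrual is even, that is 120/30 = 4 per month, or 4 × 4 = 16 more starts during the four-month wait, giving 46 if all are counted. Counting them is doubtful. The look is timed from the start of the required subjects, and protocol 9.8.1 lets accrual go on while data on the interim subjects are gathered, which treats those subjects as a separate set. The first scheduled scan is at Cycle 3 Day 1, about 8 weeks in, so subjects who started in the last 8 weeks of the wait would have no scheduled response assessment.

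**The case for a change.** The strongest case for a change is that the exact binomial is the only ORR test the plan names, and using it for the interim p-value moves the count. With A's interpolation, the exact and normal readings differ by one responder at 10 of the 20 sizes from 31 to 50. At n = 32 the exact reading gives a 3.9% chance of stopping at 45% and power of 89.2%. Even with the normal scale settled, A and C differ at 14 of those 20 sizes, by two responders at n = 50. A printed row of counts would add no patients and leave Type I error alone.

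The first part does not stand: the exact test contradicts the plan's own count at n = 30, so an analyst who checks the method against that line would discard it. The second part stands as a true statement about the text, but its effect is small near 30 and amounts to about one point of power further out.

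Nor would printing counts be neutral. A table built on an exact 2% limit for stopping at 45% keeps power at or above 90.6% for n = 30 to 50, but it gives 7 at n = 31 and 8 at n = 34, where all three normal-scale readings give 8 and 9. Compared with A, it lowers the chance of stopping at a true ORR of 30% by 13 to 14 points at n = 31, 34, 42 and 45 (for example 38.6% to 24.5% at n = 31). That is a different rule with its own trade-off. Printing A's counts instead would write in a second point, 0.025 at n = 120, that the documents do not supply for this purpose.

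**Conclusion.** The gap is real but calls for no change. The n = 30 boundary is correct and reveals its own scale. On that scale the three readings agree at four of the five sizes from 31 to 35 and differ by one responder at n = 33. Across n = 31 to 50 power lies between 89.4% and 91.5%, so the worst shortfall against the planned 90% is about 0.6 of a point. Type I error is untouched because the look can only stop for futility and the boundary is non-binding. The IDMC advises, the sponsor decides, and the charter, which is not available here, may already hold the detail.

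This rests on assumed interpolation end points, on a range of 31 to 50 chosen for illustration, and on treating investigator and independent responses as equal in the power figures. If the interim sample were far above 30 the readings would separate more (18 under A and 20 under C at n = 60), but the likely overshoot is a few subjects if those who start during the four-month wait are not counted.

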9.8.2 Final Analysis

Final analyses will be conducted approximately 6 months after the final subject receives his / her first dose.

10 STUDY ADMINISTRATION

10.1 GOOD CLINICAL PRACTICE STATEMENT

This study is to be performed in accordance with the protocol, the Declaration of Helsinki, the ICH Harmonised Tripartite Guideline for GCP, and all applicable local regulatory requirements.

10.2 INFORMED CONSENT

Verastem will provide a sample subject Informed Consent Form (ICF) for modification, as appropriate, by the Investigator. The ICF must include all elements required by ICH, GCP, and must adhere to the IRB/IEC requirements and the ethical principles that have their origin in the Declaration of Helsinki.

The Investigator or his/her staff will explain the nature of the study, its purpose and associated procedures, the expected duration, and the potential risks involved to the subject prior to enrollment. The Investigator or designee will obtain written, informed consent. The subject will have ample time and opportunity to ask questions and will be informed about the right to withdraw from the study at any time without any disadvantage and without having to provide a reason for this decision. Following the discussion regarding the study, a subject will be asked if they are willing to sign and personally date a statement of informed consent. Only if the subject voluntarily agrees to sign the informed consent statement and has done so, may he/she enter the study. A copy of the signed and dated ICF will be provided to the subject. The signed ICF is to remain in the Investigator's file, per local requirements.

The ICF and any other written information provided to the subjects will be revised whenever important new information becomes available that may be relevant to the subject's consent, or if there is an amendment to the protocol which necessitates a change to the content of the subject's informed consent. The Investigator will inform the subject of changes in a timely manner and will ask the subject to confirm continuation of their participation in the study by their signature on the revised informed consent form (if applicable). Any written ICF and written information must receive the approval/favorable opinion of the IRB/IEC in advance of use. Any additional approvals from the initial informed consent form should be forwarded to the Sponsor.

10.3 SUBJECT CONFIDENTIALITY

The written ICF will explain that study data will be stored in a database, maintaining confidentiality in accordance with national data legislation. All data processed by Verastem or its representative(s) will be identified by subject number and study code.

The written ICF will also explain that for data verification purposes, authorized representatives of Verastem, a regulatory authority, and IRB/IEC may require direct access to parts of the hospital or clinic records relevant to the study that include the subject's medical history.

The Investigator must ensure that the subjects' anonymity is maintained. On the eCRFs or other documents submitted to the Sponsor, subjects should not be identified by their names, but by their assigned subject number and study code. Documents not for submission to the Sponsor, such as signed Informed Consent Forms, should be maintained in strict confidence by the Investigator.

10.4 INSTITUTIONAL REVIEW BOARD/ ETHICS COMMITTEE REQUIREMENTS

The final study protocol, including the final version of the ICF, must be approved or given a favorable opinion in writing by an IRB/IEC at each clinical trial site. The Principal Investigator must submit written approval to Verastem before he or she can enroll any subject into the study.

The Principal Investigator is responsible for informing the IRB/IEC of any amendment to the protocol. In addition, the IRB/IEC must approve all advertising used to recruit subjects for the study. The protocol must be re-approved by the IRB/IEC annually.

Progress reports and notifications of SAEs will be provided to the IRB/IEC according to regulations and guidelines.

10.5 CASE REPORT FORMS AND SOURCE DOCUMENTATION

Electronic CRFs will be provided for the recording of all data. The Principal Investigator / Sub-Investigator or designee will record data on all observations, tests, and assessments specified in the protocol on the eCRFs provided by Verastem .

10.6 SPONSOR MONITORING

Before the first subject is enrolled into the study, a representative of Verastem will visit the study site to:

- Determine the adequacy of the facilities.
- Discuss with the Investigator(s) (and other personnel involved with the study) their responsibilities with regard to the protocol, and the responsibilities of Verastem .

During the conduct of the study, a representative of Verastem, Inc. will have regular contact with the clinical trial site, and have regular visits to the clinical trial site to:

- Provide information and support the PI.
- Confirm that the facilities remain acceptable.
- Confirm that the study team is adhering to the protocol, data are being accurately recorded in the eCRFs, and the investigational product is being properly maintained and accountability records are current.
- Perform source data verification with access to all original clinical records for each subject.

10.7 INDEPENDENT DATA MONITORING COMMITTEE

An Independent Data Monitoring Committee (IDMC) will be assembled to periodically review all available safety information and recommend whether or not the trial should continue, or should continue with modifications, based on their review of this data. In addition, the IDMC will review preliminary efficacy data at the time of the interim analysis and make a recommendation on futility of the study. All final decisions regarding study conduct will reside with the Sponsor. Membership and responsibilities of the IDMC will be documented in a separate IDMC Charter.

10.8 QUALITY ASSURANCE

In compliance with GCP and regulatory requirements, the Sponsor, a third party on behalf of the Sponsor, regulatory agencies or IRB/IECs may conduct quality assurance audits at any time during or following a study. The Investigator must agree to allow auditors direct access to all study-related documents including source documents, and must agree to allocate his or her time and the time of his or her study staff to the auditors in order to discuss findings and issues.

10.9 STUDY OR CLINICAL SITE TERMINATION

Verastem, or designee, reserves the right to terminate the study or a clinical trial site at any time. Conditions that may warrant termination of the study include, but are not limited to:

- The discovery of an unexpected, serious, or unacceptable risk to subjects enrolled in the study.
- The decision on the part of Verastem to suspend or discontinue testing or the treatment of the study drug.
- Failure of the Investigator to comply with GCP.
- Submission of knowingly false information from the clinical trial site to Verastem or regulatory authorities.
- Insufficient adherence to protocol requirements.

If terminating the study, Verastem and the Investigator(s) will assure that adequate consideration is given to the protection of the subjects' interests.

10.10 DURATION OF THE STUDY, EXPECTED DURATION OF SUBJECT PARTICIPATION, AND END OF STUDY

The study is estimated to complete enrollment within 30 months. Subjects will be followed for survival for up to 3 years after their first dose of IPI-145. The maximum number of months to complete the study is expected to be approximately 66 months.

10.11 RECORDS RETENTION

All correspondence related to this clinical study should be kept in appropriate study files. Records of subjects, source documents, eCRFs, drug inventory, IRB, and Sponsor correspondence pertaining to the study must be kept on file. All study documents must be kept secured for a period of 2 years after a marketing application is approved for IPI-145; or, until 2 years after shipment and delivery of the drug for investigational use is discontinued or as long as required by local regulations, whichever is longer. There may be other circumstances for which the Sponsor is required to maintain study records and, therefore, the Sponsor should be contacted prior to removing study records for any reason.

